## Introduction

Globally, 125 million people have psoriasis, estimating 2 to 3% of the total population [1]. Generally, first-line therapy for the treatment of mild to moderate psoriasis includes a topical regimen containing vitamin D analogues and glucocorticoids, and phototherapy. Whereas, for the treatment of moderate to severe psoriasis, systemic therapy is required, including small-molecule therapies and biologics [2-4]. However, the long-term use of systemic treatment is associated with some toxic adverse events (AEs) like nephrotoxicity, hepatotoxicity, hyperkalemia, hypomagnesemia, hypertension, tremors, malignancies, and loss of drug response [5-9]. A new treatment option is needed.

Mesenchymal stem cells (MSCs) exosome ointment, PTD 2021P, is being developed as a potential and promising treatment for the management of psoriasis. MSCs are one of the extensively employed cells in clinical trials with established safety profiles in humans and are approved for treating extremely inflexible inflammatory diseases [10, 11]. MSC exosomes are highly known for their potent immunomodulatory properties and have the potential to mitigate inflammation by promoting the secretion of anti-inflammatory cytokines, stimulating Treg polarization, and preventing complement activation [12-14].

We previously showed that topical application of MSC exosome not only reduced C5b-9 but also IL-17, and IL-23 in the IMQ-induced psoriasis mouse model [10]. As psoriatic and IMQ-treated stratum corneum is rich in activated complements and complement-activated neutrophils, and neutrophils are now implicated as the major source of IL-17 in psoriasis [15], it was postulated that topically applied MSC exosome inhibits C5b-9 formation in psoriatic and IMQ-treated stratum corneum, and this, in turn, reduces IL-17 secretion by neutrophils. When topically applied TID, the MSC exosome ointment, on mouse skin for 20 days at 10x higher than the clinical dose, the MSC exosome ointment elicited minimal systemic and local adverse effects (unpublished).

Before the conduct of this study, PTD 2021P has not been administered to humans thus far. Therefore, this phase 1 study was the first to evaluate the safety and tolerability of the application of the MSC exosome ointment with repeated topical application on adult healthy subjects (TID from Day 1 to 20). The results of this study were to provide the first clinical information on the drug's safety and inform the selection of administration of exosome ointment to be evaluated in subsequent clinical studies. The endpoints included to assess the safety and tolerability of exosome ointment for topical application in healthy adult volunteers are:

- Frequency of treatment-emergent adverse events (TEAEs)
- The incidence rate of local skin responses (LSR, i.e., erythema, flaking/scaling, crusting, swelling, vesiculation/pustulation, erosion/ulceration, hyperpigmentation, hypopigmentation, and scarring) [Time Frame: Days 1 and 21]
- Changes from baseline in blood parameters (including hematology, chemistry, and other inflammation parameters such as C-reactive protein [CRP] and erythrocyte sedimentation rate [ESR]) [Time Frame: Days 1 and 21]

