### *Identification, visual assessment, and photography of application area*

A trained expert evaluator (an Investigator or designee) identified the area of study product application and performed visual assessments which were carried out using an adapted version of SCORing Atopic Dermatitis (SCORAD) scale and visual assessment score (VAS). A photograph of the area of application was also taken using a dedicated compact digital camera at the clinic where subject visits were done.

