#### *Treatment Period*

After confirmation of the application site, the subjects applied exosome ointment along with Vesiderm liposome cream (TID per day). The study product was applied daily (Day 1 to 20) with a gap of 4 hours between each dose to an area of healthy skin (one palm size) on the forearm using 1 fingertip unit (FTU). The Vesiderm liposome cream was applied in the same area immediately after.

All through the treatment period, the subjects completed the daily Subject Diary to capture adverse events (AEs; skin-related and other), concomitant medications, and time of study product application.

Follow-up calls were made every 3 days (Days 3, 6, 9, 12, 15, and 18) to check on compliance to the investigational product's (IP), and if subjects had any adverse events or taken any concomitant medications during the period. Any AEs reported by the subject during the calls were to be referred to the investigator for appropriate review and follow-up.

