#### Safety Assessment

Safety assessment included vital signs, clinical safety laboratory tests, inflammatory blood examinations, assessment of area of application and incidence and severity of AEs.

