##### *Assessment of area of application*

The area of application was assessed by a dermatologist for parameters adapted from the SCORAD scale as shown in the next paragraph. The patient graded the subjective symptoms including itch and sleeplessness using an SCORAD scale.

This scale assessed the following:

- Intensity of reaction: The identified area of application was assessed for the intensity of signs including redness, swelling, oozing/crusting, scratch marks, skin thickening, and dryness and graded as none (0), mild (1), moderate (2) or severe (3).

- Subjective symptoms: The identified area of application was assessed for the subjective symptoms including itch and sleeplessness and graded from 0 (no itch or no sleeplessness) to 10 (worst imaginable itch or sleeplessness).

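### The LSR endpoint names nine skin responses, but the only itemised skin scale has no named item for five of them, and no other source for LSR incidence is named

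*Combined protocol and SAP*

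**What the plan says.** **Endpoint.** The Introduction of the combined protocol and SAP lists three safety endpoints. The second is the incidence rate of LSRs at Days 1 and 21. The term is introduced with *i.e.*, so the list that follows is a definition and not a set of examples: "erythema, flaking/scaling, crusting, swelling, vesiculation/pustulation, erosion/ulceration, hyperpigmentation, hypopigmentation, and scarring".

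**Instrument.** The section headed Assessment of area of application introduces the scale as follows: "The area of application was assessed by a dermatologist for parameters adapted from the SCORAD scale as shown in the next paragraph". What comes next there has the site graded for "intensity of signs including redness, swelling, oozing/crusting, scratch marks, skin thickening, and dryness", each from 0 (none) to 3 (severe). The subject also rates itch and sleeplessness from 0 to 10.

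**Other records of the skin.**
- The section on identification, visual assessment and photography names a visual assessment score (VAS) beside the adapted SCORAD, without items, and a photograph.
- The End of Study section repeats the photograph and the visual assessment, and also collects AEs.
- The Treatment Period section has a daily diary that covers skin-related AEs, and a follow-up call every 3 days.

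**Link between endpoint and data.** The Safety Assessment section lists "assessment of area of application and incidence and severity of AEs" among its components and does not mention LSRs. The term LSR is not used after the Introduction. The Statistical Analysis section promises summary tables, subject listings, and frequencies and percentages for categorical variables, without reference to this endpoint.

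**The concern.** An incidence needs a numerator, and the numerator needs a record in which each response was looked for and marked present or absent. For several of the nine responses the document describes no such record. The scale and the endpoint read as if drawn from different lists: some LSRs have no item, and some graded signs (scratch marks, skin thickening) correspond to no LSR on a natural reading.

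The Introduction says the product had not been given to humans before and that the results were to inform later studies. For a topical product, blistering, erosion, pigment change and scarring are findings that a later study would want to rely on. If the report shows 0/10 for one of them, the reader needs to know whether ten sites were inspected for it and found clear, or whether nobody was asked to record it. As written, the document does not allow that distinction.

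**Working it through.** No sample-size or power figure bears on this point, and the plan gives no figure to reproduce. The check is a mapping of the nine endpoint responses (Introduction) onto the six graded signs (Assessment of area of application).

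| LSR in the endpoint | Closest graded sign | Quality of match |
|---|---|---|
| Swelling | Swelling | Same term |
| Erythema | Redness | Synonym |
| Crusting | Oozing/crusting | Combined item |
| Flaking/scaling | Dryness | Reasonable, not identical |
| Erosion/ulceration | Scratch marks or oozing | Only on a loose reading |
| Vesiculation/pustulation | Oozing | Only on a loose reading |
| Hyperpigmentation | None | No match |
| Hypopigmentation | None | No match |
| Scarring | None | No match |

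Itch and sleeplessness match none of the nine. Unmatched responses, accepting matches cumulatively from strict to lenient:

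1. Stand-alone items only (swelling, erythema): 9 − 2 = 7; 7/9 = 78%.
2. Add crusting: 9 − 3 = 6; 6/9 = 67%.
3. Add flaking/scaling as dryness (central reading): 9 − 4 = 5; 5/9 = 56%.
4. Add erosion/ulceration as scratch marks or oozing: 9 − 5 = 4; 4/9 = 44%.
5. Add vesiculation/pustulation as oozing (most lenient): 9 − 6 = 3; 3/9 = 33%.

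Hyperpigmentation, hypopigmentation and scarring are unmatched at every step.

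Next, whether another described record fills the gap:

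- **VAS.** Named once, with no items and no stated link to LSRs.
- **Photographs.** Taken at the clinic; no reading or scoring rule is given.
- **Diary and AE reports.** They cover skin-related events, but the Adverse events section assigns the diary to the frequency of treatment-emergent AEs, which is a separate endpoint.

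Any of these could hold the information. None is named as the source of LSR incidence.

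A minor point concerns the two time points. With 10 subjects, each one is worth 1/10 = 10 percentage points. A sign graded mild on both days in one subject gives 1/10 = 10% if the count is of signs present on Day 21, and 0/10 = 0% if it is of signs new or worse since Day 1. For graded signs, listings that show both visits' grades would let a reader derive either figure.

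**The case against.** The strongest reply is that the document does not close the list. The graded signs are introduced by the word *including*, the scale is described as adapted, the VAS items are not given, and Study Design refers to a clinical protocol approved by the review board, so the study forms may have held more items. In addition, the Day 21 visit combined a visual assessment, a photograph and AE collection, on top of a daily diary and regular calls. Visible blistering, ulceration or scarring on a small forearm site had several routes into the AE data.

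Much of this stands. A reader might infer that the five responses were never examined; the document does not support that, and AE capture is a real safeguard. What remains is that the document introduces the scale parameters as those shown in its next paragraph, the unmatched responses are not among them, and no other record is tied to the endpoint.

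It is also fair that the count depends on the mapping. Five is the central reading; only three is independent of any choice of synonym.

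Two further inferences are tempting and should not be drawn:

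- **That the absence of an event rule is itself an error.** The 0–3 grade gives a natural none-versus-any threshold, the stated time frame can be read as incidence at each visit, the product went "to an area of healthy skin (one palm size) on the forearm", and subject listings were planned.
- **That the sections disagree on who assessed the skin.** One says "A trained expert evaluator (an Investigator or designee) identified the area of study product application and performed visual assessments", another a dermatologist. A dermatologist can be the investigator or designee, so these are compatible.

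**Conclusion.** The endpoint and the described instrument do not match. Five of nine LSRs (56%) have no named item on the only itemised skin scale. Three of nine (33%) have none under any mapping: hyperpigmentation, hypopigmentation and scarring. No other record is named as the source, so the assessment as written cannot supply the stated endpoint for those responses.

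The mismatch in the text is firm. The count of five assumes that redness stands for erythema, the combined oozing item for crusting and dryness for flaking/scaling, and that scratch marks and oozing do not stand for erosion or vesiculation. The conclusion is limited to what this document states and does not extend to what was done at the visits.

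This should be fixed because it governs how a zero on a stated safety endpoint can be read. It does not undermine the AE endpoint or the laboratory endpoint.

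**What to change.** The document is written in the past tense and appears to describe completed data collection, so the practical steps are:

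1. If the VAS or another study form listed the unmatched responses, give its items and cite it as the source of LSR incidence.
2. If not, keep the nine-response endpoint, report each ungraded response as *not assessed* rather than 0/10, and limit conclusions on those responses to what the AE data support.
3. Label any scoring of the Day 1 and Day 21 photographs as post hoc.
4. As a minor addition, report each response at Day 1 and at Day 21, with new-or-worse responses shown separately. For graded signs this can be derived from the subject listings.

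The cost is a source column, a label and a short table. Optional photograph scoring would cover about 10 × 2 = 20 images, assuming one per subject per visit.

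If data were still to be collected, the Day 1 pre-application and Day 21 skin assessments should record all nine responses, as present/absent or on the existing 0–3 grade, and the Statistical Analysis section should name that record as the source. Adding the five unmatched responses costs 5 × 2 × 10 = 100 form entries. Giving flaking/scaling its own item makes 6 × 2 × 10 = 120, and splitting crusting from oozing as well makes 7 × 2 × 10 = 140. No new visit or procedure is needed.

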## Materials and Methods

### Study Design

The trial was conducted under a clinical trial authorization (Authorisation No.: CTA2200019) approved by the Health Sciences Authority (HSA) Singapore. The clinical protocol and informed consent form (ICF) were approved by the National Healthcare Group Domain Specific Review Board (NHG DSRB reference number: 2021/00905).

This study was conducted in accordance with the protocol and consensus ethical principles derived from international guidelines including the Declaration of Helsinki, Council for International Organizations of Medical Sciences (CIOMS) International Ethical Guidelines, applicable International Conference on Harmonization (ICH), Good Clinical Practice (GCP) Guidelines, and other applicable laws and regulations.

This was a Phase 1, single center, open-label study. After signing an ICF, subjects underwent screening procedures on Day 1 prior to the first study product application to determine eligibility. Once eligible, all subjects (n=10) received topical treatment with the MSC exosome ointment immediately followed by Vesiderm liposome cream TID on the forearm with a gap of 4 hours between doses.

The study consisted of the following periods:

- A Screening Period of 1 day (Day 1)
- A Treatment Period of 20 days (Day 1 to 20)
- An End of Study (EOS) Period of 1 day (Day 21 [+3 days]).

### *Screening Period*

#### Screening

The subjects were screened for eligibility on Day 1 prior to the application of the study product. Subjects were asked to sign the ICF after having the study described to them. After obtaining written informed consent, subjects underwent the following screening procedures for participation in the study:

- Inclusion/exclusion criteria assessments
- Vital signs
- Medical history
- Demographic data review
- Standard hematology panel
- Renal panel
- Liver function test
- Inflammatory blood examinations
- Pregnancy test (if applicable)
- Concomitant medications

### *Identification, visual assessment, and photography of application area*

A trained expert evaluator (an Investigator or designee) identified the area of study product application and performed visual assessments which were carried out using an adapted version of SCORing Atopic Dermatitis (SCORAD) scale and visual assessment score (VAS). A photograph of the area of application was also taken using a dedicated compact digital camera at the clinic where subject visits were done.

#### *Treatment Period*

After confirmation of the application site, the subjects applied exosome ointment along with Vesiderm liposome cream (TID per day). The study product was applied daily (Day 1 to 20) with a gap of 4 hours between each dose to an area of healthy skin (one palm size) on the forearm using 1 fingertip unit (FTU). The Vesiderm liposome cream was applied in the same area immediately after.

All through the treatment period, the subjects completed the daily Subject Diary to capture adverse events (AEs; skin-related and other), concomitant medications, and time of study product application.

Follow-up calls were made every 3 days (Days 3, 6, 9, 12, 15, and 18) to check on compliance to the investigational product's (IP), and if subjects had any adverse events or taken any concomitant medications during the period. Any AEs reported by the subject during the calls were to be referred to the investigator for appropriate review and follow-up.

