#### Dosage

MSC exosome ointment (70 µg MSC exosomes/g ointment) was the study intervention to be administered. It was administered as a topical intervention of one FTU per one hand area on the forearm (average hand area was 160-200 cm^2), thrice a day for 20 days.

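### Does describing the treated area as a palm in one place and a hand in another undermine the local skin response results?

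*Combined protocol and SAP*

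**What the plan says.** The combined protocol and SAP describes the application in two places.

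- Treatment Period: the ointment goes "to an area of healthy skin (one palm size) on the forearm using 1 fingertip unit (FTU"), three times a day on Days 1 to 20. No size in cm² is attached to the palm.
- Dosage: a "topical intervention of one FTU per one hand area on the forearm", at the same frequency and for the same 20 days, with the ointment at 70 µg exosomes per gram. Here a size is given: the "average hand area was 160-200 cm"².

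Other sections bear on how the area was handled. Under Identification, visual assessment, and photography of application area, a trained evaluator "identified the area of study product application and performed visual assessments", and the site was photographed. Treatment began after the site had been confirmed. The End of Study section repeats the photograph and the visual assessment. Under Assessment of area of application, "The identified area of application was assessed for the intensity of signs", each graded 0 to 3.

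The Introduction lists "The incidence rate of local skin responses" among the endpoints and says the results are to "inform the selection of administration of exosome ointment to be evaluated in subsequent clinical studies". The Statistical Analysis section provides descriptive summaries only.

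**The concern.** For a topical product, local tolerability is normally judged against the amount of product on each square centimetre of skin. If the same fingertip unit is spread over a palm without fingers rather than a whole hand, the skin receives more per cm². The two sections use different anatomical terms, neither says whether fingers are included, and no section equates the terms. The evaluator's identification of the site is described without any measurement of it.

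This is the first administration to humans, local skin responses are an endpoint, and later studies will draw on the results. A reader could reasonably worry that an observed incidence belongs to an unknown surface exposure, and that a later study could treat a given area more heavily than this one did while appearing to follow the same regimen.

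**Working it through.** The documents state no product-per-cm² figure, so there is none to reproduce. The check asks how far the two readings can differ and whether the difference enters any result.

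**Inputs from the documents**

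- Amount per application: 1 FTU (Treatment Period and Dosage).
- Frequency and duration: 3 a day for 20 days (both sections).
- Concentration: 70 µg/g (Dosage).
- Hand area: 160-200 cm² on average (Dosage).

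**Assumed, because the documents do not give them**

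- Palm share of the hand area, f: 1.0 if the terms are synonyms; 0.6 or 0.5 if the palm excludes the fingers.
- FTU mass, m: 0.25-0.6 g.

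**Step 1: total amount.** Applications = 3 × 20 = 60, each of 1 FTU, under either section. The ratio of total amount between readings is 1.0.

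**Step 2: product per cm².** Surface exposure per application = m × 70 / area, with palm area = f × hand area. The palm-to-hand ratio of surface exposure is 1/f, and m cancels.

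| f | Area (cm²) | µg/cm² per gram of FTU | Ratio to hand |
|---|---|---|---|
| 1.0 | 160-200 | 70/200 = 0.350 to 70/160 = 0.438 | 1.00 |
| 0.6 | 96-120 | 70/120 = 0.583 to 70/96 = 0.729 | 1.67 |
| 0.5 | 80-100 | 70/100 = 0.700 to 70/80 = 0.875 | 2.00 |

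The stated hand range alone moves exposure by 200/160 = 1.25-fold. The widest spread across readings is 200/80 = 2.5-fold.

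**Step 3: would one agreed term settle the exposure?** No. The assumed FTU masses alone move the absolute value by 0.6/0.25 = 2.4-fold. On the hand reading, exposure runs from 0.25 × 70/200 = 0.087 to 0.6 × 70/160 = 0.263 µg/cm² per application. Fixing the area term removes one of two unknowns.

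**Step 4: does the area enter a result?** The incidence is the number of subjects with a response divided by 10. Neither the count nor the denominator is scaled by area. Signs are graded on whatever site the evaluator identified. There is one arm and one regimen, so no comparison exists that a difference in area could bias. Adverse events and blood parameters are likewise summarised per subject.

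**Step 5: do the two sections contradict each other?** Set side by side, they describe the same act: same product, same amount, same limb, same schedule. One gives a term with a size, the other a term without one. Reading both as a single area of 160-200 cm² violates neither. No figure in one section conflicts with a figure in the other.

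**The case for a change.** The strongest case for acting is that surface exposure is what gives local tolerability its meaning, and the area is the one element the two sections word differently. Nothing elsewhere closes the gap. The evaluator step mentions no measurement, a photograph is not a value in cm², and the diary items listed under Treatment Period do not include area. If palm and hand were meant differently, the skin could have received up to about twice the product per cm² that a reader of the Dosage section would infer. Clarifying would cost a sentence.

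Much of this stands. The terms do differ, the palm has no stated size, and product per cm² cannot be fixed from the text. It would also be wrong to say that area is irrelevant to skin reactions: a heavier film could produce more of them. But the reported incidence would still describe what was applied to these 10 subjects. The uncertainty concerns carrying that incidence to another surface exposure, which this study does not attempt.

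The claim that neither term is defined does not stand, since the Dosage section sizes the hand area. Nor is material inconsistency shown: every ratio above 1.0 comes from an assumed palm share. The practical remedy is limited too. The text reports the study in the past tense, so a Day 1 area measurement appears no longer obtainable, and the subject instructions, which may already define the area, are not among the documents.

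**Conclusion.** This is a minor gap in wording that does not call for a change to the design or analysis. The amount per application and the 60 applications are the same in both sections. The local skin response incidence and the descriptive summaries come out the same whichever area term is used. The possible difference in product per cm² is none if the terms are synonyms, and 1.67- to 2.0-fold if the palm is assumed to be 0.6 to 0.5 of the hand. The documents supply no basis for choosing among these, and the unstated FTU mass would leave the absolute exposure open even with one agreed term.

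The Treatment Period and Dosage sections should be reconciled by the clinical team, who alone can say what area was meant. A sensible report would state the area treated and the FTU mass, or say that the area was not recorded. That is ordinary care in reporting and alters no result.

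The conclusion rests on two features of the plan: a single arm with one regimen, and no endpoint expressed per unit of skin area. In a study comparing surface doses, the same ambiguity would matter.
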